5. INDUCTION CHEMOTHERAPY

5.1 mFOLFIRINOX

After study enrollment, patients will receive (or continue with) mFOLFIRINOX (omission of bolus 5FU) as outlined below, allowing for modifications of dose and schedule as per clinical judgment of patient's treating physician. For patients who have received FOLFIRINOX chemotherapy including a 5FU bolus prior to study entry, once consent is signed, the 5FU bolus must be omitted. Because of its improved safety profile without sacrificing efficacy, mFOLFIRINOX is commonly administered in the treatment of pancreatic cancer (31). Modified FOLFIRINOX regimen with improved safety and maintained efficacy in pancreatic adenocarcinoma. *Pancreas* 2013 Nov 42(8):1311-5.

mFOLFIRINOX may be administered in a community practice setting as long as the treating oncologist assumes responsibility for all reporting and follow-up requirements.

Prophylactic growth factors may be administered at any time before, during, or after chemotherapy cycles. It is recommended that the patient be evaluated at one of the participating centers every 3-6 months. As standard practices are changing and Leucovorin is not widely used, we will allow the omission of this drug during both induction and treatment phases of the study.

mFOLFIRINOX to complete a total of 4 cycles, (1 cycle = 14 days)

- Oxaliplatin 85 mg/m² IV over 2 hours on Day 1, followed by
 - Irinotecan 180 mg/m² IV over 90 minutes on Day 1, followed by
 - Leucovorin* 400 mg/m² IV over 2 hours on Day 1, followed by
 - 5FU** 2,400 mg/m² IV over 46 – 48 hours
- *Leucovorin may be administered concurrently with the last 30 minutes of oxaliplatin, and the entire 90 minutes of irinotecan.
- **5FU is administered via infusion only; there is no bolus injection of 5FU.

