7.1 Chemotherapy following SBRT

For patients randomized to SBRT, mFOLFIRINOX should resume within 8 weeks following completion of SBRT. If this schedule cannot be met, the subject may continue treatment "off protocol" and as recommended by the treating Medical Oncologist or according to local standard of care. These patients will be followed for overall survival and progression-free survival. Subsequent data analysis will be performed on an intention-to-treat basis.

Dosing and modification guidelines for mFOLFIRINOX are provided in Section 9, **however, chemotherapy schedule modifications and dose reductions are allowed and are left to the discretion and clinical judgment of the treating medical oncologist.** A total of at least 6 cycles of mFOLFIRINOX is recommended but the total number of cycles

is left to the clinical judgement of the treating oncologist. As standard practices are changing and Leucovorin is not widely used, we will allow the omission of this drug during both induction and treatment phases of the study.

Participating centers at all times should follow the Study Calendar (Section 14) and ensure that all records and study materials are collected and reported properly.

Since mFOLFIRINOX is an accepted standard of care, chemotherapy may be administered in a community setting as long as the treating oncologist assumes responsibility for the follow up care and reporting requirements. It is recommended that the patient be evaluated at a participating site every 3-6 months.

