7.5 Criteria for Removal from Study

Patients will be withdrawn from the study for any of the following reasons:

- disease progression (as defined in Section 15.1.2 Disease Parameters)
- patient withdrawal
- pregnancy
- patient noncompliance, or failure of the patient to follow instructions of the study staff
- protocol director decides that continuing participation could be harmful to the patient
- treatment needed for patient that is not allowed in the study
- patient is deemed resectable and proceeds to surgery
- study cancellation
- other administrative reasons
- unanticipated circumstances.

Patients will continue mFFX on-study until one of these endpoints; in the event of intolerable toxicity from mFFX, subjects will still be followed per protocol although chemotherapy may be altered or discontinued, the decisions of which will be left to the treating Medical Oncologist.

Patients withdrawn from the study will be followed for overall survival only.

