9.1 Modified Folfirinox (mFFX) Dosing

Modified Folfirinox dosing is below, **however modifications of dose and schedule are allowed as per clinical judgment of patient's treating medical oncologist.** Recommendations for toxicity management are in Section 9.1.1.

mFOLFIRINOX, 1 cycle = 14 days

- Oxaliplatin 85 mg/m² IV over 2 hours on Day 1, followed by
- Irinotecan 180 mg/m² IV over 90 minutes on Day 1, followed by
- Leucovorin* 400 mg/m² IV over 2 hours on Day 1, followed by
- 5FU** 2,400 mg/m² IV over 46 – 48 hours

*Leucovorin may be administered concurrently with the last 30 minutes of oxaliplatin, and the entire 90 minutes of irinotecan

**5FU is administered via infusion only; there is no bolus injection of 5FU

Subjects should be assessed for Adverse Events (AEs) once during each chemotherapy cycle, and AEs should be recorded in the AE Tracking Form in Appendix V. Serious Adverse Events (SAEs) should be reported promptly as according to the guidelines in this protocol. (See Section 11 for more information regarding documenting and reporting SAEs and AEs.)

Chemotherapy infusion records should be kept in the patient's study chart, either with

the Medication Administration Record (MAR) or other clinic records which contain: Date of infusion, dose completed of each agent, modifications if any and reason for modification with supporting source documents as needed. Laboratory results prior to infusion should also be supplied in the patient study chart, as well as the consultation note if the patient is seen by the treating physician.

Laboratory results and administration dates and doses of each agent should also be entered into REDCap.

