15.1.5 Progression-Free Survival (or other time-to-event parameters)

The criteria for time to progression and progression-free survival (PFS) will be the time from randomization to documented progression or death. Individuals will be censored at the date of last evaluation for progression if neither event is observed. Overall survival will be defined as time from randomization until death from any cause. Participants will be censored at the date of last contact if the date of death is not observed. Local PFS will be the duration from randomization to local progression or death if death occurs before local progression. Metastasis free survival will be the duration from randomization to metastasis or death from any cause, if death occurs before metastasis. Individuals will be censored at the time of the last evaluation for local or distant progression, respectively, if neither progression nor death is observed.

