17.4 Plan of Analysis

Demographic and clinical characteristics of patients and the characteristics of treated lesions (volume, location, and modality) will be summarized by means, medians, standard deviations, ranges and proportions as applicable.

Time to event outcomes (overall survival, metastasis free survival, and progression free survival) will be summarized using Kaplan-Meier curves and medians with 95% confidence intervals calculated using Greenwood's formula. Cox proportional hazards models will be used to compare treatment groups and to assess risk factors (e.g. biologic markers and PET volume). The effect of site will be tested in the Cox models; the effect of whether or not the patients received Leucovorin will also be tested in the Cox models. The level of response (and other categorical outcomes) will be tabulated at each follow-up interval. Logistic regression and Cox models will be used to assess the proportion with a response category depending upon the level of censoring prior to the annual visit.

The measurements of the volume of the pancreatic tumors based upon CT and PET-CT scans will be compared using paired t-tests or Wilcoxon signed-rank tests as appropriate. The agreement between pancreatic tumor measurements will be compared among the three institutions using correlation coefficients, percentage agreement, and inter-correlation coefficients.

Quality of life outcomes will be assessed at each time interval and compared using the recommended guidelines from the module. Differences in QOL for the two treatment groups will be explored using a repeated measures model in order to account for the within-patient correlation. Special interest will be placed on exploring the aspects of QOL which are known to be impacted by SBRT.

At this time all research on biomarkers for disease progression is exploratory. The goal is to potentially identify biomarkers that are associated with disease progression. Should any biomarkers be identified, their impact on the time to event outcomes will be summarized using Kaplan Meier curves and they will be tested using Cox proportional hazards models.

Quality of life at each interval will be calculated and compared using the recommended guidelines from the module (available by E-mail: [contact]). Efficacy outcomes with repeated measurements over time (e.g. quality of life) will be analyzed using a generalized estimating equation (GEE) approach to account for within-patient

correlation.

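### Leucovorin receipt is undefined in the Cox models and can change after randomization, so a single yes/no value per patient is open to time-related bias in either direction

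*Combined protocol and SAP*

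**What the plan says.** Section 17.4 (Plan of Analysis) uses Cox models to compare the treatment groups and to assess risk factors. It adds that "the effect of whether or not the patients received Leucovorin will also be tested in the Cox models". It does not define receipt: not the phase, not the number of cycles, not ever versus always, and not whether the covariate is fixed or time-dependent. No landmark or time-dependent method appears anywhere in the document.

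Four other sections bear on this:

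- **Exposure can vary.** Leucovorin is part of the listed regimen from induction on (Sections 5.1 and 9.1). Sections 5.1 and 7.1 both state that "we will allow the omission of this drug during both induction and treatment phases of the study".
- **Time origin.** Section 15.1.5 says that PFS "will be the time from randomization to documented progression or death". Randomization follows induction and re-staging (Sections 5.2 and 5.3). Overall survival and metastasis-free survival start at the same point.
- **Exposure opportunity.** Section 7.5 lists disease progression among the removal criteria and says "Patients will continue mFFX on-study until one of these endpoints".
- **Data.** Section 9.1 says that "administration dates and doses of each agent should also be entered into REDCap".

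**The concern.** A Cox model with a fixed covariate treats that covariate as known at time zero. A yes/no flag built from post-randomization cycles is not known then. A patient who stays progression-free longer goes through more cycles, and so has more chances for the flag to change. The flag then partly measures the outcome it is supposed to explain, which is the structure of immortal-time bias.

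The plan sets out to test the effect of a drug whose omission it expressly permits. A spurious hazard ratio, in either direction, would be read as evidence on that permission. Because receipt is undefined, an analyst could also settle the definition after seeing the data, and different reasonable definitions give opposite answers.

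**Working it through.** **1. The plan's own figures.** The inputs are from Section 17.3.2: medians of 6 and 10.2 months, 86 patients per arm, 60 months of accrual, at least 12 months of follow-up, exponential PFS, two-sided 0.05. With rate λ = ln 2 / median, the probability of an event is 1 − [exp(−12λ) − exp(−72λ)] / (60λ).

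- mFFX arm: λ = 0.1155, probability 0.964, × 86 = 82.9 events.
- SBRT arm: λ = 0.0680, probability 0.893, × 86 = 76.8 events.
- Total 159.7. Section 17.5.2 states 83 + 77 = 160.
- True hazard ratio 6/10.2 = 0.588. Schoenfeld power = Φ(√(159.7/4) × |ln 0.588| − 1.96) = Φ(1.39) = 91.8%. The Freedman version gives 90.6%. The plan states 91%.

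The design reproduces. The plan gives no figure for the leucovorin test.

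**2. Why the flag follows survival.** Suppose a patient not on leucovorin at randomization starts it with probability p in each 14-day cycle. After k cycles the chance of being coded *ever received* is 1 − (1 − p)^k. At p = 5% this is 1 − 0.95² = 10% for a patient who progresses after 2 cycles, and 1 − 0.95¹² = 46% for one who reaches 12 cycles (168 days). The reverse holds for a user who stops with probability 5% per cycle: the chance of still being coded *never omitted* falls from 0.95² = 90% to 0.95¹² = 54%. So under the first definition long survivors drift into the exposed group, and under the second they drift out of it.

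**3. Size under a null drug.** The stated design was simulated with leucovorin having no effect. Baseline use, switching rates and number of cycles are assumptions. The documents give none of them.

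With 50% exposed at randomization and up to 12 post-randomization cycles:

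| Definition of the fixed flag | Change per cycle | Null HR |
|---|---|---|
| Ever received, induction counted | 5% start | 0.80 |
| Ever received, induction counted | 10% start | 0.61 |
| Never omitted | 5% stop | 1.26 |
| No switching, or status at randomization | – | 1.00 |

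With 50% exposed, cycles continuing to progression (at most 26), and the first post-randomization cycle at 0.5 to 2 weeks (mFFX arm) or 4 to 8 weeks (SBRT arm), 400 trials per setting:

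| Coding | Change per cycle | Null HR | Trials rejecting at 0.05 |
|---|---|---|---|
| Ever received, induction counted | none start | about 1.0 | about 5% |
| Ever received, induction counted | 1 / 2 / 5 / 10% start | 0.87 / 0.77 / 0.55 / 0.30 | 13 / 36 / 89 / 99% |
| Ever received, post-randomization cycles only | none | 0.89 | 11% |
| Never omitted | 1 / 2 / 5% stop | 1.15 / 1.32 / 1.84 | 17 / 39 / 88% |
| Status at randomization | all settings | 0.99 to 1.02 | 2 to 6% |
| Time-dependent, on from first leucovorin cycle | all settings | 0.99 to 1.02 | 4 to 7% |

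The third row shows some bias without any switching. Patients who progress before their first post-randomization cycle are counted as unexposed.

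**4. Sensitivity.** With 12 cycles and the first one at randomization, *ever received* gives 0.84 and 0.71 at 5% and 10% starting, with rejection in 19% and 43% of trials. With only two post-randomization cycles counted, it gives 0.97 to 1.00, with rejection of 4% to 8%, at 5% to 20% starting per cycle.

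**5. The SBRT comparison.** In models containing arm and leucovorin, the SBRT hazard ratio was 0.57 to 0.61 across settings, against the true 0.588.

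**The case against.** The strongest reply is that the plan never says the covariate is fixed. It says only that the effect will be tested, and a competent analyst could code it at randomization or as time-dependent without departing from Section 17.4. That is correct: the defect is an undefined covariate, not a stated wrong method. It does not remove the point, because the literal reading is one value per patient and nothing in the plan rules that out.

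A reader might infer that the test will make an inert drug look protective. The documents do not support that. Leucovorin is in the regimen from induction, and the text describes leaving it out rather than starting it late. If receipt includes induction and nobody starts later, there is no bias. If receipt means never omitted, the bias goes the other way.

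A reader might also infer that the SBRT hazard ratio is distorted. Section 17.4 does not say that leucovorin enters the primary treatment model, and the simulations showed almost no movement. They assumed a null drug and equal switching in both arms, so they do not cover every case, but no distortion was demonstrated.

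Finally, the size depends on how many cycles count. The Study Calendar (Section 14) has a column for two post-randomization cycles, and on that count alone the bias is negligible. That stands as a lower bound. The same calendar lets patients continue maintenance chemotherapy, and Section 7.5 continues it to progression or another removal criterion, so longer exposure is within the plan.

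Leucovorin is not an objective or an endpoint, and it plays no part in the sample size or the interim rule. That limits the weight of the point.

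**Conclusion.** The concern holds in a limited form. If Section 17.4 is carried out as written, with a single yes/no value per patient that uses post-randomization cycles, the leucovorin hazard ratio is open to immortal-time bias. Neither the direction nor the size can be fixed from the documents. For a null drug the bias is below 1 for *ever received* when some patients first get it after randomization, above 1 for *never omitted* when some patients stop it, and absent when status counted from induction does not change. The illustrative 0.80, 0.61 and 1.26 rest on the assumed 50% exposure, 12 cycles and 5% or 10% switching. Fewer cycles shrink them towards 1 and more cycles enlarge them.

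It would go too far to say that the test is wrong by construction, that leucovorin will appear protective, or that the primary SBRT result is compromised. What is affected is a secondary covariate test.

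**What to change.** In Section 17.4, define the leucovorin covariate in one of two ways:

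- status during induction, known at randomization, stating whether any cycle or every cycle is required; or
- post-randomization leucovorin as a time-dependent covariate, built from the administration dates in REDCap.

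Add a sentence that post-randomization leucovorin receipt is not included in the primary SBRT treatment-effect model. Either coding brought the null hazard ratio back to 0.99 to 1.02 in every setting run. Both remain non-randomized comparisons and should be reported as associations.

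The cost is SAP wording. Section 9.1 already requires dates and doses of each agent, and the Study Calendar asks for induction infusion records, so no new data, patients or procedures are needed. This is a free improvement.

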2.3 Quality of Life Assessment

The major potential benefit of combining SBRT with chemotherapy for locally advanced pancreatic tumors is to improve local control and palliation of symptoms related to local progression of these tumors. In addition, radiosurgical ablation of the primary tumor can theoretically prevent distant seeding from the pancreatic tumor itself. Ultimately, these improvements in the treatment of pancreatic cancer may translate into an improved quality of life and overall survival.

Quality of life will be assessed using The European Organization for Research and Treatment in Cancer quality of life core cancer questionnaire with the pancreatic cancer module (EORTC QLQ C-30/ PAN26). The European Organization for Research and Treatment in Cancer Quality of Life Questionnaire (EORTC QOL-C30) is a multidimensional, 30-item questionnaire which assesses five functional scales (physical, role, cognitive, emotional and social), three symptom scales (fatigue, pain and nausea/vomiting), a global health /QOL scale, as well as 6 single items (18). The EORTC QLQ-PAN26 supplements the core questionnaire with 26 items specific for patients with pancreatic cancer (19, 20). These instruments have been validated in patients receiving treatment for metastatic and resected pancreatic cancer and are sensitive to identify treatment related changes in quality of life. The quality of life of patients in this study will be directly compared between the 2 randomized arms. These questionnaires were also used in our previous phase II multi-institutional study evaluating SBRT and gemcitabine in patients with locally advanced pancreatic cancer.

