6. RADIATION TREATMENT PLANNING AND SBRT ADMINISTRATION

6.1 Pre-SBRT Tests, Procedures, and Planning

The following will be completed **prior to SBRT**:

- a) Consultation with medical history and physical examination.
- b) Pathology with report confirming malignancy.
- c) Labs: CBC with differential, CMP (Comprehensive Metabolic Panel) and CA199. CEA is optional. Additionally, up to 20ml of additional blood may be drawn for research purposes (study bloods may also be collected in follow-up visits). For specific information regarding collection and processing, see Section 12.1 Laboratory Correlative Studies.
- d) Seed placement: Gold fiducial seed placement percutaneously, intraoperatively, or under endoscopic ultrasound guidance, which may be performed prior to study enrollment. In some patients, an optional additional core biopsy may be obtained for research purposes if consent is provided by the patient, and may be done at the time of fiducial implantation (See Section 12.1, Laboratory Correlative Studies) or in a separate procedure. For patients who are planned to be treated with active breathing coordinator (ABC) or 4D kV CBCT IGRT, fiducial seed placement is optional.
- e) Scans: CT or MR. PET/CT scan is recommended though not required.
- f) Signed informed consent.
- g) Negative Pregnancy Test (urine or serum) for females of childbearing potential OR menopausal as defined in Appendix III – Definition of Menopausal Status.
- h) Eligibility confirmation.
- i) Study registration and randomization.
- j) Quality of Life Survey: Baseline collection of EORTC QLQ C-30/ PAN26 QOL.

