- j Follow-up appointments 1 month before or after will be permitted, e.g. for 6-month follow-up, visit, labs, scan and QOL surveys can be done at 5-7 months.
- k 4-6 week follow-up visit and corresponding activities are *optional* and may be added if clinically indicated.

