17.1.2 Secondary Endpoints

- To compare the one year progression-free survival in pancreatic cancer patients following chemotherapy alone or chemotherapy and SBRT.
- To compare metastasis free survival in pancreatic cancer patients following chemotherapy alone or chemotherapy and SBRT.
- To compare the overall survival in pancreatic cancer patients treated with chemotherapy alone or chemotherapy and SBRT.
- To compare local progression-free survival in pancreatic cancer patients after chemotherapy +/- SBRT.
- To evaluate acute (within 3 months of treatment) grade 2 or greater gastritis, fistula, enteritis, or ulcer and any other grade 3-4 gastrointestinal toxicity within 3 months of treatment.
- To identify new biomarkers in pancreatic cancer.
- To evaluate the quality of life of patients before and after either chemotherapy alone or chemotherapy and SBRT.

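### Section 17.4 names no baseline term in the quality-of-life model, so a baseline score the trial already collects may go unused and the arm comparison may be less precise than it could be

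*Combined protocol and SAP*

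**What the plan says.** Section 17.4 describes the QOL analysis in two places. The first reads "Quality of life outcomes will be assessed at each time interval and compared using the recommended guidelines from the module", followed by "Differences in QOL for the two treatment groups will be explored using a repeated measures model in order to account for the within-patient correlation". The second reads "Quality of life at each interval will be calculated and compared using the recommended guidelines from the module", followed by "Efficacy outcomes with repeated measurements over time (e.g. quality of life) will be analyzed using a generalized estimating equation (GEE) approach". None of these sentences names a covariate, change from baseline, an arm-by-visit term, or whether the baseline questionnaire is an outcome row. The module guidelines are cited but not reproduced.

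A baseline is collected. Section 6.1 lists "Quality of Life Survey: Baseline collection of EORTC QLQ C-30/ PAN26 QOL" as item j, and the calendar in section 14 marks QOL at study enrollment, ahead of randomization. Later questionnaires fall at 3, 6, 9 and 12 months after study treatment and then every 6 months, with an optional early visit. The window is wide: "for 6-month follow-up, visit, labs, scan and QOL surveys can be done at 5-7 months".

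An arm comparison is intended. Section 2.3 states: "The quality of life of patients in this study will be directly compared between the 2 randomized arms". The secondary endpoint in section 17.1.2 is "To evaluate the quality of life of patients before and after either chemotherapy alone or chemotherapy and SBRT".

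**The concern.** A patient's later QOL score usually depends in part on where that patient started. A model that leaves the baseline score out carries that between-patient variation as noise in the arm difference. The score is already in the database, so using it costs no data.

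Precision will be scarce. Section 7.5 makes progression a reason for withdrawal, after which patients are followed for survival only. On the design medians of section 17.3.2 (6 and 10.2 months, exponential), the progression-free proportions 12 months after randomization are 2^(-12/6) = 25% and 2^(-12/10.2) = 44%. Many patients will therefore contribute only a few follow-up scores.

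There is also a conditional risk. If the baseline row stays among the repeated outcomes and one arm effect is reported over all rows, that effect averages in a time point at which a true pre-randomization score has no expected arm difference.

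**Working it through.** **The plan's own figures.** No power, standard deviation, effect size or correlation is stated for QOL, so there is no QOL figure to reproduce. The PFS design, which supplies the patient numbers, does reproduce. With λ = ln 2/median and event probability 1 − (e^(−12λ) − e^(−72λ))/(60λ), 86 patients per arm give 82.9 + 76.8 = 159.7 events (stated: 83 + 77 = 160). At 160 events and hazard ratio 6/10.2 = 0.588, power is 91.9% by Schoenfeld and 90.6% by Freedman (stated: 91%). Nothing below touches this.

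**Assumptions, none from the documents.** Correlation ρ between any two scores of a patient (compound symmetry), SD 1, m equally weighted follow-up scores, constant arm effect, no missing scores.

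**Formulas, per patient.**
- Follow-up scores only: V0 = (1 + (m − 1)ρ)/m.
- With baseline as covariate: V1 = V0 − ρ². For m = 1 the ratio V1/V0 is 1 − ρ².
- Baseline kept as an outcome, one arm main effect: expected effect = true effect × m/(m + 1), with variance (1 + mρ)/(m + 1).

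Worked case, m = 2 and ρ = 0.5: V0 = 1.5/2 = 0.75; V1 = 0.75 − 0.25 = 0.50; ratio 0.67.

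| Follow-up scores m | V1/V0, ρ = 0.3 | ρ = 0.5 | ρ = 0.7 | Effect left if baseline is pooled into one arm effect |
|---|---|---|---|---|
| 1 | 0.91 | 0.75 | 0.51 | 1/2 = 50% |
| 2 | 0.86 | 0.67 | 0.42 | 2/3 = 67% |
| 4 | 0.81 | 0.60 | 0.37 | 4/5 = 80% |

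At m = 1 and ρ = 0.5, the unadjusted comparison needs 1/0.75 = 1.33 times as many patients for the same precision.

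**Power illustration.** Assumed effect 0.4 SD, m = 2, ρ = 0.5, two-sided 0.05; SE = √(2V/n).

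| Analysis | 86 per arm | 43 per arm (half lost) |
|---|---|---|
| Follow-up scores only | 86% | 57% |
| Baseline as covariate | 96% | 75% |
| Baseline as outcome, one arm effect | 57% | 33% |

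**Simulation check.** GEE, 300 runs, exchangeable correlation, 86 per arm, same settings.

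| Analysis | Mean estimate | SD of estimate | Power |
|---|---|---|---|
| Follow-up scores only | 0.39 | 0.135 | 83% |
| Baseline as covariate | 0.38 | 0.104 | 96% |
| Baseline as outcome, one arm effect | 0.26 | 0.133 | 55% |
| Baseline as outcome, arms constrained equal there | 0.38 | 0.104 | 96% |

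The first two rows centre on the same value, so leaving baseline out costs precision and does not bias the estimate. The last row shows that keeping baseline as an outcome is harmless when the arms are constrained equal at that time.

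**The case against.** The strongest reply is that the plan is silent and has not made a wrong choice. A reader might infer that 17.4 commits the trial either to raw follow-up scores or to baseline as one of the repeated outcomes. The text does not support that. A repeated measures or GEE model can carry a baseline covariate, and the before-and-after wording of the endpoint suggests that baseline will be used somehow. The cited module guidelines may address baseline too; they are not in the documents, so this cannot be checked. This objection stands: the loss is a risk that the text leaves open.

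A reader might also infer that the arm comparison is biased, or is diluted whenever baseline is an outcome row. Neither follows. Dilution needs one arm effect averaged over visits that include baseline. It does not arise with arm-by-visit contrasts read at follow-up or with the arms constrained equal at baseline.

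The gain could also be small. Enrollment may precede all four 14-day induction cycles (8 weeks), and follow-up is timed from the end of study treatment, so the correlation could be low. At ρ = 0.2 and one follow-up score the saving is only 0.2² = 4%. This stands as a limit on size.

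Finally, QOL differences are to be explored, with no QOL power claim or decision rule. That keeps the point minor. It does not remove it, because section 2.3 promises a direct comparison of the arms and the improvement is nearly free.

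**Conclusion.** The point holds as a low-cost improvement. Section 17.4 names no baseline term for a between-arm QOL comparison although a baseline score is collected. Without one, the comparison of follow-up scores remains unbiased by the omission but loses precision: adjustment would cut the variance by 9% to 49% for one follow-up score at ρ from 0.3 to 0.7, and by more with several scores. These figures rest on assumed correlations and compound symmetry. Dilution to 50%, 67% or 80% of the effect is confined to the one specification described above and assumes equal weights.

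Baseline also needs a definition. The calendar places the questionnaire at enrollment, while section 6.1 lists it after the randomization item. A reader might infer from 6.1 that baseline is taken after allocation, but that list covers everything due before SBRT and need not be in time order. The two places should still be reconciled, because the covariate must be measured before randomization in both arms.

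The primary PFS analysis is not affected. Loss of QOL data after progression or withdrawal is a separate matter that baseline adjustment does not solve.

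**What to change.** In section 17.4:

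- Define the baseline QOL score as the one collected before randomization (the enrollment questionnaire in the calendar), and reconcile section 6.1 with this.
- For each scale, model post-randomization scores with that scale's baseline score as a covariate and with arm, visit and arm-by-visit terms. An equivalent option keeps baseline as an outcome with the arms constrained equal at baseline.
- Report adjusted arm differences at the follow-up visits with confidence intervals. Do not report a single arm effect averaged over rows that include baseline.
- Give priority to the QOL aspects that 17.4 already singles out as affected by SBRT. Section 2.3 counts 5 + 3 + 1 + 6 = 15 scales and items in the QLQ-C30 alone, before PAN26.
- Merge the two QOL descriptions in 17.4 into one.

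The cost is a few sentences in 17.4 and a consistency edit in 6.1, with no new data, visits or patients.
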